The primary hypothesis is that the efficacy of these treatments will depend upon an individual subject's baseline characteristics. For SR we expect that baseline measures of "excessive time spent in bed" may predict response and for CT we expect that baseline measures of cognitive arousal and pain may predict response. Exploratory analyses using signal detection techniques will systematically compare and contrast the potential usefulness of a number of additional potential moderator measures. Insomnia is a serious health problem in Gulf War Veterans that is often associated with extensive prescription of sleeping medications. Although safer, even the latest "sleeping pills" can lead to cognitive impairment and risk of abuse. Thus non-pharmacological treatments for insomnia have been pursued as alternatives to medications. Cognitive Behavior Therapy for Insomnia (CBT-I) is the term widely used to describe therapies that combine behavioral and cognitive therapies for insomnia. The combined CBT-I approach has well-documented efficacy. Between 2012 and 2014 over 650 VA mental health clinicians have received extensive training in CBT-I. Although CBT-I is efficacious, the optimal target populations for its major components has not yet been well-defined for Gulf War Veterans. We propose to address this gap and develop tools for clinicians to identify the best treatment for insomnia for individual Gulf War Veterans.

c) Explain why human subjects must be used for this project. (i.e. purpose of study is to test efficacy of investigational device in individuals with specific condition; purpose of study is to examine specific behavioral traits in humans in classroom or other environment)

This is a study of insomnia in humans.

2. Study Procedures

a) Please SUMMARIZE the research procedures, screening through closeout, which the research participant will undergo. Sections in the protocol attached in section 16 can be referenced, BUT do not copy the clinical protocol. Be clear on what is to be done for research and what is part of standard of care. For research involving collaborators, please specify the respective roles of Stanford and each

Title : Predictors of Response to Insomnia Treatments for Gulf War Veterans
Approval Period: 08/31/2024 - 08/31/2025

collaborator on the protocol.

Our hypotheses will be tested in a randomized parallel groups design. Randomization will be based on type of treatment assignment: either to SR or CT.

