After screening and randomization in the 2-week baseline phase, subjects will receive SR or CT in the 6-week treatment phase. Participants will have the option to complete study sessions over telehealth for the entirety of the 6 weeks. There will be no more treatment after this point. At the end of the 6-week treatment, subjects will return to repeat many of the psychological tests administered during baseline to determine the short-term benefit. This 4-year proposal will include 100 subjects (2 groups of 50 each) with outcome, mediator and moderator measures collected at appropriate points.

All subjects will receive education about basic sleep hygiene as well as information about the science of sleep including sleep stages and sleep regulation.

Sleep Restriction Therapy (SR). The initial Time in Bed (TIB) prescription is calculated on the average total sleep time (TST) reported in the baseline sleep logs.

After one week, depending on subject's daily sleep logs, the therapist suggests a new TIB prescription. Napping is neither prescribed nor proscribed. However, if subjects find themselves very sleepy (not just tired, but actually sleepy) they are advised to take a brief (15 to 30 minutes) nap to ensure their safety.

Cognitive Therapy (CT). The CT treatment module is designed to meet three general goals:

1) identification of dysfunctional sleep cognitions, 2) challenging their validity, and 3) replacing them with more adaptive substitutes.

Several specific techniques designed to meet these goals are discussed

in materials distributed to subjects. Similar to SR, subjects in CT are given information about relevant elements of the science of sleep and healthy sleep practices.

We will also continue to monitor progress post-treatment in the follow-up period. The complete package of outcome measures will be repeated at the follow-up session. We will tell subjects that we expect the benefits of treatment to continue and/or improve with time and we will also encourage subjects to continue practicing the treatment instructions to maintain their progress after active treatment ends.

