Subjects will be screened for eligibility via a phone interview and an in person or telehealth evaluation. Subjects that learn about the study through StudyPages campaign ads and are recruited through the study landing page developed by StudyPages. They will complete a brief pre-screening survey to confirm interest and screen for initial inclusion criteria before being contacted by our study team for a full phone interview. The in-person or telehealth evaluation may be split into two visits if necessary.

Title : Predictors of Response to Insomnia Treatments for Gulf War Veterans
Approval Period: 08/31/2024 - 08/31/2025

At the in-person or telehealth evaluation, after signing a consent form, a more detailed interview about sleep problems, and medical and psychiatric history will be obtained by the Duke Structured Sleep Interview, including evaluations of cognitive impairment and depression. Exclusion criteria will further be evaluated by the following given solely at the office evaluation: Acute/Unstable Chronic Illness checklist, Columbia Suicide Severity Rating Scale (C-SSRS), DUKE Structured Sleep Interview, Hamilton Depression Rating Scale (HDRS24), Life Stressor Checklist, Mini International Neuropsychiatric Interview Version 5 (MINI), Montreal Cognitive Assessment (MOCA) or MOCA-Blind, Morningness-Eveningness Questionnaire, and the Sleep Related Behavior Questionnaire. Subjects will additionally be set up with PSG equipment. The PSG will be completed in the subject's own home and be used to screen a for Obstructive Sleep Apnea and Periodic Limb Movement Disorder.

Subjects will return to the lab the next morning to have the equipment removed.

Participants will be evaluated on the Anxiety and Preoccupation about Sleep Questionnaire (APSQ), Depression Anxiety and Stress Scale (DASS-21), Epworth Sleepiness Scale, and the Insomnia Severity Index each visit during weeks 1-8, and again at week 32. Sleep logs will be done daily during weeks 1-8, and again at week 32. The following will be done at weeks 1, 8, and 32: AUA8 Nocturia; Brief Pain Inventory short form (BPI-SF); Beck Anxiety Inventory (BAI); Beck Depression Inventory (BDI); Clinician Administered PTSD Scale (CAPS); Dysfunctional Beliefs and Attitudes about Sleep Scale; AUA8 (DBAS); Glasgow Content of Thoughts; Glasgow Sleep Effort Scale; Multidimensional fatigue Inventory; Penn State Worry Questionnaire (PSWQ); Perceived Stress Scale (PSS); SF-36 (RAND).

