Subjects will be evaluated on Functional Outcomes of Sleep Questionnaire at weeks 1, 2, 8 and 32.

Subjects will be evaluated on the Sleep Associated Monitoring Index (SAMI) at weeks 1 and 8.

Subjects will be evaluated on the Trial Making Test, Color Word Interference test, Thought Control Questionnaire Insomnia-Revised (TCQI), and the RBANS at weeks 1 and 32.

Following the completion of treatment at week 7, subjects will complete the Treatment Adherence Survey, Treatment Satisfaction Survey and Working Alliance Inventory. The Working Alliance Inventory will also be given at the second treatment session (week 3). If participants are participating in Telehealth, they will complete these questionnaires as RedCap surveys on Stanford's RedCap.

Blood will be drawn to measure levels of C-reactive protein (CRP). Urine samples will be collected at during each of the 3 study phases to monitor abstain from drugs of abuse, except for medical marijuana used less than four times a week. Samples will be collected by nurses at the VA Clinical Studies Unit and analyzed by the VA lab. Blood samples will be taken at the same time to be analyzed for C-reactive protein. Remaining blood will be banked to be analyzed for genetic factors.

Due to the COVID-19 pandemic, we are adding the option for participants to complete all study sessions through telehealth. We will utilize Zoom and send questionnaires as RedCap surveys on Stanford's RedCap. This will allow the participants to move forward in the study while also not deviating from the study timeline. We will still collect adverse events and study measures at each treatment session. After the COVID-19 shut-down is over, we will still offer telehealth as an option to our veterans to be flexible to their scheduling needs and keep consistency with the measures taken during

Title : Predictors of Response to Insomnia Treatments for Gulf War Veterans
Approval Period: 08/31/2024 - 08/31/2025

this crisis. Under normal circumstances, we will allow the veterans to choose if they would like to utilize telehealth or in-person treatment session and would complete all therapy sessions through the selected delivery method. We will document each individual who started therapy sessions in-person and switched to telehealth so that we can do analyses to see if their data is viable.

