Criteria for discontinuation of a patient in the study will include an increase in bothersome nightmares for a week under treatment. We have not seen consistent reporting of nightmares with the proposed treatments, however that is always possible, hence we would want to make sure that nightmares occurred for at least a week before a patient was discontinued. Patients will be allowed to continue in the protocol after an SAE independent of treatment, e.g. hospitalization following a fall. All treatments are considered active and patients will be allowed to continue their treatment as a courtesy. However, data from such subjects will not be included in statistical analyses since such SAEs may affect sleep. Patients will not be restarted if their sleep deteriorates meeting the above criteria and they are discontinued from the protocol.

7. Indicate to whom the data and safety monitoring person, board, or committee will disseminate the outcome of the review(s), e.g., to the IRB, the study sponsor, the investigator, or other officials, as appropriate.

Serious Adverse Events are reported to the IRB using the standard reporting forms.

8. Select One:

The Protocol Director will be the only monitoring entity for this study.

This protocol will utilize a board, committee, or safety monitor as identified in question #2 above.

10. Benefits

a) **Describe the potential benefit(s) to be gained by the participants or by the acquisition of important knowledge which may benefit future participants, etc.**

Some participants may find that their sleep is improved.

11. Privacy and Confidentiality

Privacy Protections

a) **Describe the setting and method (e.g. crowded waiting room, patient exam room, telephone or email**

Title : Predictors of Response to Insomnia Treatments for Gulf War Veterans
Approval Period: 08/31/2024 - 08/31/2025

communication) in which interactions will occur and how the privacy interests of participants will be maintained. Note, high risk data such as PHI must be sent via "Secure:" email per Stanford policy.

During screening, participants will meet in a private interview room with a member of the study team to sign the consent form, discuss the protocol, and determine suitability for enrollment. All interviews will be done in a private setting. Samples will be obtained in a private setting.

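### Randomised participants with an SAE unrelated to treatment are dropped from the analyses as whole subjects, because the event may affect the outcome

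*Protocol*

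**What the plan says.** The rule sits in the Data Safety and Monitoring Plan, Section 9(e), item 6, not in a statistical section. It first states: "Patients will be allowed to continue in the protocol after an SAE independent of treatment, e.g. hospitalization following a fall". It adds that "patients will be allowed to continue their treatment as a courtesy", and then that "data from such subjects will not be included in statistical analyses since such SAEs may affect sleep". No time window is given, and nothing limits the rule to data after the event or to one analysis. No other part of the protocol defines an analysis set that keeps these participants.

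Section 2(a) places randomisation in the two-week baseline phase, before the six-week treatment phase, so an SAE on treatment or in follow-up comes after randomisation. Of the end of the treatment phase it says: "There will be no more treatment after this point". The end-of-treatment questionnaires are timed as "Following the completion of treatment at week 7".

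Sleep data are collected repeatedly. The schedule gives the "Insomnia Severity Index each visit during weeks 1-8, and again at week 32", and "Sleep logs will be done daily during weeks 1-8, and again at week 32".

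Section 1(b) sets the main question: "The primary hypothesis is that the efficacy of these treatments will depend upon an individual subject's baseline characteristics". Section 8(a)(ii) now expects 50-55 participants, against the 100 in Section 2(a).

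**The concern.** The exclusion depends on something that happens after randomisation, and the reason given is that it may change sleep, which is what the trial measures. Randomisation then no longer guarantees that the analysed groups are comparable. This affects the SR-CT contrast and also the moderator analyses that carry the primary hypothesis.

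Three features make it worse.

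- **Breadth.** An SAE cannot have affected sleep logs or Insomnia Severity Index (ISI) scores recorded before it, yet the wording drops those as well.
- **Judgement.** Someone must decide that an SAE is unrelated to treatment. Section 9(e) has the Protocol Director review all SAEs and act as sole monitor, and it names no criteria for that decision. The protocol's own example is a fall, while Section 9(a)(iv) accepts that SR can make participants sleepy, so the call may not be neutral between arms.
- **Unclear window.** The sentence about courtesy treatment suggests SAEs during treatment. The sentence about staying in the protocol is wider and could cover follow-up. Under the wider reading, a week-8 outcome recorded before a later SAE is lost too.

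At stake are possible bias in both analyses and certain loss of valid data from a sample already about half its planned size.

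**Working it through.** The protocol gives no SAE rate, SD, effect size or power, so there is no figure of its own to reproduce. The rates and gaps below are assumptions used for scale. From the protocol come 50-55 participants (taken as 25 per arm), visits in weeks 1-8 and at week 32, and a six-week treatment phase.

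**1. Benchmark.** The standard error of the SR-CT contrast in SD units is sqrt(2/25) = 0.283. With residual SD 1, the arm-by-moderator slope per SD of the moderator has the same standard error.

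**2. Bias in the SR-CT contrast.** Let p1 and p2 be the shares excluded per arm, and d the amount by which excluded participants do worse.

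- Gap measured against retained participants: bias = (p1 - p2) x d. Low end: (0.05 - 0) x 0.5 = 0.025. High end: (0.15 - 0.05) x 1.0 = 0.10.
- Gap measured against the full-arm mean: bias = [p1/(1-p1) - p2/(1-p2)] x d. Low end: 0.0526 x 0.5 = 0.026. High end: (0.1765 - 0.0526) x 1.0 = 0.124.
- Equal p and equal d in both arms: bias = 0.

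**3. How timing changes this.** Suppose SAEs are spread evenly over weeks 1-32, a span of 31 weeks.

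- Week 8, wider reading, gap caused by the SAE: only 7/31 = 0.226 of the SAEs precede week 8. Bias is 0.025 x 0.226 = 0.006 up to 0.124 x 0.226 = 0.028 SD.
- Week 32, with the rule limited to on-treatment SAEs and the assumed rates covering all 31 weeks: the share is 6/31 = 0.194. Bias is 0.025 x 0.194 = 0.005 up to 0.10 x 0.194 = 0.019, so about 0.005 to 0.02 SD.

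The 0.03-0.12 range therefore fits week 32 under the wider reading, or rates that all arise on treatment.

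**4. Bias in the moderator slope.** For a standard-normal moderator X and logistic SAE risk p(X), bias = d x [Cov(p1(X), X) - Cov(p2(X), X)].

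- Odds ratio 1.5 per SD, 5% vs 0%, d = 0.5: 0.010.
- Odds ratio 2 per SD, 15% vs 5%, d = 1.0: 0.051.
- Risk unrelated to X, or equal between arms: 0.

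**5. Precision.**

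- Participants lost: 0.05 x 50 = 2.5 up to 0.10 x 55 = 5.5. If 5-10% is the rate over weeks 1-32 and only on-treatment SAEs count: 2.5 x 0.194 = 0.5 up to 5.5 x 0.194 = 1.1.
- Gross rise in standard error = 1/sqrt(1 - f): 1.026 at f = 0.05 and 1.054 at f = 0.10.
- Keeping these participants also adds variance, by a factor 1 + d²p(1-p). The net cost of exclusion is 1/sqrt[(1-p)(1 + d²p(1-p))]. For d = 1.0 this is 1.002 (p = 0.05) and 1.010 (p = 0.10). For d = 0.5 it is 1.020 and 1.042.

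**6. Data recorded before the SAE.** With one ISI per week in weeks 1-8 and an SAE evenly placed between weeks 2 and 8, the scores already recorded number 2, 3, 4, 5, 6 or 7, a mean of 4.5 of 8. The first two are baseline, so the mean post-baseline loss is 4.5 - 2 = 2.5 of 6.

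**The case against.** The strongest reply has four parts.

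- **Intended meaning.** The sentence stands in a safety answer on an IRB form and gives an effect on sleep as its reason, so it may mean only data after the SAE. That is possible, but the text refers to subjects and sets no such limit. Even on that reading, outcomes are discarded because of a post-randomisation event.
- **No bias if the condition is met.** If the SAEs really are unrelated to treatment, exclusion rates differ between arms only by chance, and the larger scenarios require misclassification. The retained set might also be said to estimate the effect in the absence of SAEs. The first point is fair and is why zero bias is stated as a possible result. The second does not rescue the rule: the protocol states no such aim, and that aim would not call for deleting measurements made before the event.
- **Size.** Even the largest contrast bias is under half the standard error, the net precision cost is only about 0.2-4.2%, some of the lost ISI scores are baseline, and the protocol does not commit to analysing the intermediate weekly scores. All of this stands and limits the claim.
- **Timing.** Section 8(m)(iii) shows analysis already under way, so changing the rule now could itself look driven by results. This is a real risk, and the fix must deal with it openly.

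**Conclusion.** The concern holds. The protocol states a whole-subject exclusion after randomisation, linked to the outcome and without a time limit. This is a rule the protocol fixes, not a detail left to a statistical analysis plan; a plan that kept all randomised participants would contradict it.

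The likely numerical effect is modest and rests wholly on assumed SAE rates and outcome gaps. Bias is zero under balance. Otherwise it is up to about 0.12 SD for the contrast and 0.05 for the moderator slope, against a standard error of about 0.28, and it is smaller at week 8 or if only on-treatment SAEs count. The loss is anywhere from about half a participant to 6 of 50-55. The trial is not invalidated, but the rule gives up the protection of randomisation for a reason that cannot justify its breadth. It should be fixed.

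**What to change.** Delete the exclusion sentence from Section 9(e), item 6. State instead that all randomised participants are analysed in their assigned group with all collected data, including data after an SAE, for both the SR-CT comparison and the moderator analyses. Report the present rule (SAE subjects left out) alongside as a labelled sensitivity analysis; censoring only post-SAE data can be added as another.

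Because analysis has begun, date and document the change and state whether outcomes by arm had been seen. No change is proposed to continuation of treatment after an SAE or to the discontinuation criterion.

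The cost is one amendment to the analysis set and at least one extra analysis, with no new data collection. Pre-SAE data already exist; post-SAE data exist only for participants who continued. The downsides are somewhat noisier outcomes and a late change that must be shown not to depend on results.

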13.1 Consent

22-AUG-2022 Gulf War Insomnia Consent

Check if VA related Y

a) Describe the informed consent process. Include the following.

- i) Who is obtaining consent? (The person obtaining consent must be knowledgeable about the study.)
- ii) When and where will consent be obtained?
- iii) How much time will be devoted to consent discussion?
- iv) Will these periods provide sufficient opportunity for the participant to consider whether or not to participate and sign the written consent?
- v) What steps are you taking to minimize the possibility of coercion and undue influence?
- vi) If consent relates to children and if you have a reason for only one parent signing, provide that rationale for IRB consideration.

(i) The persons obtaining consent will be one of the investigators, the study coordinator, or a research assistant, who have been trained to give informed consents. (ii) The consenting interview is always done after the potential research subject has been presented with a description of the study and indicated interest in participating, and before any information is collected, or any questionnaires answered. The consenting interview typically takes place in one of the private interview rooms in the Aging Clinical Research Center. For telehealth sessions, the consent process will be completed through Zoom. Study staff will review the consent with the participant. If the participant agrees, they will sign the consent form through a fillable PDF form in Adobe. Study Staff will share the screen with participants and participants will take control of the screen to sign the form. Participants will be sent a copy of the signed consent form. If the participant is unable to attend the consenting interview on a computer, multiple copies of the consent form will be mailed to them in advance. The participant will have the physical consent form in front of them while the study staff reviews the consent form. The participant will be provided a pre-paid return envelope to mail one signed copy of the consent form back to the VA. (iii) Enough time will be allowed for the consent discussion for the potential participant to make an informed decision, and to ask any and all questions they may have and discuss the study with the researchers. We estimate this will take between 30 minutes and one hour. (iv) The potential participant may take the consent home to discuss with family or others, and return later to sign it if they so desire. (v) Every attempt will be made to ensure the participant does not feel coerced. Participants are allowed as much time as needed to discuss the project with the research staff. If desired by the participant, the signing of the consent is delayed for as long as needed to allow participants to discuss the project with family, personal health care providers, or others. We believe that the payment offered for participation is not great enough to entice a person to participate if they do not want to do so. (vi) Not applicable.

b) What is the Procedure to assess understanding of the information contained in the consent? How will the information be provided to participants if they do not understand English or if they have a hearing impairment? See HRPP Chapter12.2 for guidance.

The potential subject will be asked questions about the study to make sure they understand. All participants will have a good understanding of English, since the standardized forms, questionnaires, and tests used are not currently available in other languages. Hearing impairment severe enough to impair comprehension is an exclusion criteria for a similar reason.

c) What steps are you taking to determine that potential participants have the capacity to participate in the decision-making process? If your study may enroll adults who are unable to consent, describe (i) how you will assess the capacity to consent, (ii) what provisions will be taken if the participant regains the capacity to consent, (iii) who will be used as a legally authorized representative, and (iv) what provisions will be made for the assent of the participant.

We expect all persons who meet inclusion criteria will have capacity to give informed consent.

Title : Predictors of Response to Insomnia Treatments for Gulf War Veterans
Approval Period: 08/31/2024 - 08/31/2025

Additional VA questions:

i) **List the people to whom you have formally delegated responsibility to obtain informed consent, and state whether they have the appropriate training to perform this activity.**

The persons obtaining consent will be one of the investigators, the study coordinator, or a research assistant, all of whom have been trained to give informed consents. All staff have completed the required training in Human Subjects, Good Clinical Practice, and HIPAA.

ii) **Will legally effective informed consent be obtained from the participant or the participant's legally authorized representative (LAR) or both? If LAR, is it clear who can serve as LAR?**

Consent will be obtained from the participant.

iii) **Will the circumstances of the consent process minimize the possibility of coercion or undue influence and provide the prospective participant or their representative sufficient opportunity to consider whether to participate?**

Participants are allowed as much time as needed to discuss the project with the research staff. If desired by the participant, the signing of the consent is delayed for as long as needed to allow participants to discuss the project with family, personal health care providers, or others.

iv) **Will the circumstances of the consent process minimize the possibility of coercion or undue influence?**

Participants are allowed as much time as needed to discuss the project with the research staff. If desired by the participant, the signing of the consent is delayed for as long as needed to allow participants to discuss the project with family, personal health care providers, or others.

v) **Will the information being communicated to the participant or the representative during the consent process exclude any exculpatory language through which the participant or the representative is made to waive or appear to waive the participant's legal rights, or release or appear to release the investigator, the sponsor, the institution, or its agent from liability for negligence (e.g. I give up any property rights I may have in bodily fluids or tissue samples obtained in the course of the research)?**

All information presented to the participant, including anything they must sign, has been approved by the IRB.

vi) **Please confirm the following:**

- A witness to the participant's signature or the participant's legally authorized representative's signature will sign and date the consent document.**
- If the sponsor or the IRB requires a witness to the consenting process in addition to the witness to the participant's signature and if the same person is needed to serve both capacities, a note to that effect is placed under the witness's signature line.**
- A copy of the signed and dated consent document will be given to the person signing the consent document.**
- The consent form is on the VA Form 10-1086.**

